5.4.2 Eliciting Adverse Event Information

A consistent methodology of non-directive questioning should be adopted for eliciting adverse event information at all patient evaluation timepoints. Examples of non-directive questions include the following:

"How have you felt since your last clinic visit?"

"Have you had any new or changed health problems since you were last here?"

5.4.3 Specific Instructions for Recording Adverse Events

Investigators should use correct medical terminology/concepts when reporting AEs or SAEs. Avoid colloquialisms and abbreviations.

5.4.3.1 Diagnosis versus Signs and Symptoms

If known at the time of reporting, a diagnosis should be reported rather than individual signs and symptoms (e.g., record only liver failure or hepatitis rather than jaundice, asterixis, and elevated transaminases). However, if a constellation of signs and/or symptoms cannot be medically characterized as a single diagnosis or syndrome at the time of reporting, it is acceptable to report the information that is currently available. If a diagnosis is subsequently established, it should be reported as follow-up information.

5.4.3.2 Deaths

All deaths that occur during the protocol-specified AE reporting period (see Section 5.2.2), regardless of attribution, will be reported to the appropriate parties. When recording a death, the event or condition that caused or contributed to the fatal outcome should be reported as the single medical concept. If the cause of death is unknown and cannot be ascertained at the time of reporting, report "Unexplained Death".

5.4.3.3 Preexisting Medical Conditions

A preexisting medical condition is one that is present at the start of the study. Such conditions should be reported as medical and surgical history. A preexisting medical condition should be re-assessed throughout the trial and reported as an AE or SAE only if the frequency, severity, or character of the condition worsens during the study. When reporting such events, it is important to convey the concept that the preexisting condition has changed by including applicable descriptors (e.g., "more frequent headaches").

5.4.3.4 Hospitalizations for Medical or Surgical Procedures

Any AE that results in hospitalization or prolonged hospitalization should be documented and reported as an SAE. If a patient is hospitalized to undergo a medical or surgical procedure as a result of an AE, the event responsible for the procedure, not the procedure itself, should be reported as the SAE. For example, if a patient is hospitalized to undergo coronary bypass surgery, record the heart condition that necessitated the bypass as the SAE.

- An event that leads to hospitalization under the following circumstances should not be reported as an adverse event or a serious adverse event:
 - Planned hospitalization required by the protocol (e.g., for study drug administration or insertion of access device for study drug administration)
 - Hospitalization for a preexisting condition, provided that all of the following criteria are met:
 - The hospitalization was planned prior to the study or was scheduled during the study when elective surgery became necessary because of the expected normal progression of the disease
 - The patient has not experienced an adverse event

An event that leads to hospitalization under the following circumstances is not considered to be a serious adverse event, but should be reported as an adverse event instead:

- Hospitalization that was not necessary because of the patient requirement for outpatient

5.4.3.5 Assessment of Severity of Adverse Events

The adverse event severity grading scale for the NCI CTCAE (v5.0) will be used for assessing adverse event severity. Table 2 will be used for assessing severity for adverse events that are not specifically listed in the NCI CTCAE.

Table 2 Adverse Event Severity Grading Scale for Events Not Specifically Listed in NCI CTCAE

Grade	Severity
1	Mild; asymptomatic or mild symptoms; clinical or diagnostic observations only; or intervention not indicated
2	Moderate; minimal, local, or non-invasive intervention indicated; or limiting age-appropriate instrumental activities of daily living ^a
3	Severe or medically significant, but not immediately life-threatening; hospitalization or prolongation of hospitalization indicated; disabling; or limiting self-care activities of daily living ^{b, c}
4	Life-threatening consequences or urgent intervention indicated ^d
5	Death related to adverse event ^d

NCI CTCAE = National Cancer Institute Common Terminology Criteria for Adverse Events.

Note: Based on the most recent version of NCI CTCAE (v5.0), which can be found at:

http://ctep.cancer.gov/protocolDevelopment/electronic_applications/ctc.htm

- ^a Instrumental activities of daily living refer to preparing meals, shopping for groceries or clothes, using the telephone, managing money, etc.
- ^b Examples of self-care activities of daily living include bathing, dressing and undressing, feeding oneself, using the toilet, and taking medications, as performed by patients who are not bedridden.
- ^c If an event is assessed as a "significant medical event," it must be reported as a serious adverse event (see Section 5.4.2 for reporting instructions), per the definition of serious adverse event in Section 5.2.2.
- ^d Grade 4 and 5 events must be reported as serious adverse events (see Section 5.4.2 for reporting instructions), per the definition of serious adverse event in Section 5.2.2.

5.4.4 Assessment of Causality of Adverse Events

Investigators should use their knowledge of the patient, the circumstances surrounding the event, and an evaluation of any potential alternative causes to determine whether an adverse event is considered to be related to the study drug, indicating "yes" or "no" accordingly. The following guidance should be taken into consideration (see also Table 3):

- Temporal relationship of event onset to the initiation of study drug
- Course of the event, with special consideration of the effects of dose reduction, discontinuation of study drug, or reintroduction of study drug (as applicable)
- Known association of the event with the study drug or with similar treatments
- Known association of the event with the disease under study
- Presence of risk factors in the patient or use of concomitant medications known to increase the occurrence of the event
- Presence of non-treatment-related factors that are known to be associated with the occurrence of the event

Table 3 Causal Attribution Guidance

Is the adverse event suspected to be caused by the study drug on the basis of facts, evidence, science-based rationales, and clinical judgment?	
YE	There is a plausible temporal relationship between the onset of the adverse event and administration of the study drug, and the adverse event cannot be readily explained by the patient's clinical state, intercurrent illness, or concomitant therapies; and/or the adverse event follows a known pattern of response to the study drug; and/or the adverse event abates or resolves upon discontinuation of the study drug or dose reduction and, if applicable, reappears upon re-challenge.
NO	An adverse event will be considered related, unless it fulfills the criteria specified below. Evidence exists that the adverse event has an etiology other than the study drug (e.g., preexisting medical condition, underlying disease, intercurrent illness, or concomitant medication); and/or the adverse event has no plausible temporal relationship to administration of the study drug (e.g., cancer diagnosed 2 days after first dose of study drug).

For patients receiving combination therapy, causality will be assessed individually for each protocol-mandated therapy.

5.4.4.1 Pregnancies

If a female patient becomes pregnant while receiving tenecteplase or within 90±14 days after the last dose of tenecteplase, a report should be completed and expeditiously submitted to Genentech, Inc. Follow-up to obtain the outcome of the pregnancy should also occur.

Abortion, whether accidental, therapeutic, or spontaneous, should always be classified as serious, and expeditiously reported to Genentech as an SAE. Similarly, any congenital anomaly/birth defect in a child born to a female patient exposed to the tenecteplase should be reported to Genentech, Inc. as an SAE.

5.4.4.2 Post-Study Adverse Events

The investigator should expeditiously report any SAE occurring after a patient has completed or discontinued study participation if attributed to prior tenecteplase exposure. If the investigator should become aware of the development of cancer or a congenital anomaly in a subsequently conceived offspring of a female patient who participated in the study, this should be reported as an SAE.

Case Transmission Verification will be performed by both parties during this period to ensure successful transmission of Single case reports.

CASE TRANSMISSION VERIFICATION OF SINGLE CASE REPORTS

The Sponsor agrees to conduct the Case Transmission verification to ensure that all single case reports have been adequately received by Genentech via [name] emailing Genentech a Quarterly line-listing documenting single case reports sent by [name] to Genentech in the preceding time period.

Tenecteplase–Icahn School of Medicine at Mount Sinai
Protocol ML42492

31

The periodic line-listing will be exchanged within seven (7) calendar days of the end of the agreed time period. Confirmation of receipt should be received within the time period mutually agreed upon.

If discrepancies are identified, the Sponsor and Genentech will cooperate in resolving the discrepancies. The responsible individuals for each party shall handle the matter on a case-by-case basis until satisfactory resolution. The sponsor shall receive reconciliation guidance documents within the 'Activation Package'.

Following Case Transmission Verification, single case reports which have not been received by Genentech shall be forwarded by [name] to Genentech within five (5) calendar days from request by Genentech.

At the end of the study, a final cumulative Case Transmission Verification report will be sent to Genentech.

AEs of Special Interest (AESIs)

AESIs are a subset of Events to Monitor (EtMs) of scientific and medical concern specific to the product, for which ongoing monitoring and rapid communication by the Investigator to the Sponsor is required. Such an event might require further investigation in order to characterize and understand it. Depending on the nature of the event, rapid communication by the trial Sponsor to other parties (e.g., Regulatory Authorities) may also be warranted.

Adverse events of special interest for this study include the following:

- Cases of potential drug-induced liver injury that include an elevated ALT or AST in combination with either an elevated bilirubin or clinical jaundice, as defined by Hy's law:
- Treatment-emergent ALT or AST $> 3 \cdot \text{ULN}$ in combination with total bilirubin $> 2 \cdot \text{ULN}$
- Treatment-emergent ALT or AST $> 3 \cdot \text{ULN}$ in combination with clinical jaundice
- Data related to a suspected transmission of an infectious agent by the study drug (STIAMP), as defined below:

Any organism, virus, or infectious particle (e.g., prion protein transmitting transmissible spongiform encephalopathy), pathogenic or non-pathogenic, is considered an infectious agent. A transmission of an infectious agent may be suspected from clinical symptoms or laboratory findings that indicate an infection in a patient exposed to a medicinal product. This term applies only when a contamination of the study drug is suspected.

Exchange of Single Case Reports

[name] will be responsible for collecting all protocol-defined Adverse Events (AEs)/Serious Adverse Events (SAEs), AEs of Special Interest (AESIs), Special Situation Reports (including pregnancy reports) and Product Complaints (with or without an AE) originating from the Study for the Product.

Tenecteplase–Icahn School of Medicine at Mount Sinai
Protocol ML42492

32

Investigators must report all the above-mentioned single case reports adequately to Genentech within the timelines described below. The completed MedWatch forms should be faxed/mailed immediately upon completion to Genentech at the following contacts:

All protocol-defined AEs, SAEs, AESIs, Special Situation Reports (including pregnancy reports) and Product Complaints with an AE should be sent to:

[contact]

Email: [contact]

All Product Complaints without an AE should be sent to:

[contact]

It is understood and agreed that the Sponsor will be responsible for the evaluation of AEs/SAEs, AESIs, Special Situation Reports (including pregnancy reports) and Product Complaints (with or without an AE) originating from the study. [MR{SF2}]

These single case reports will be exchanged between the parties as outlined below so that regulatory obligations are met.

- **SADRs**

Serious AE reports that are related to the Product shall be transmitted to Genentech within fifteen (15) calendar days of the awareness date.

- **Other SAEs**

Serious AE reports that are unrelated to the Product shall be transmitted to Genentech within thirty (30) calendar days of the awareness date.

- **AESIs**

AESIs requiring expedited reporting shall be forwarded to Genentech within fifteen (15) calendar days of the awareness date.

Relevant follow-up information should be submitted to Genentech Drug Safety as soon as it becomes available.

- **Special Situation Reports**

- **Pregnancy reports**

While such reports are not serious AEs or Adverse Drug Reactions (ADRs) per se, as defined herein, any reports of pregnancy (including pregnancy occurring in the partner of a male study subject), where the fetus may have been exposed to the Product, shall be transmitted to Genentech within thirty (30) calendar days of the awareness date. Pregnancies will be followed up until the outcome of the pregnancy is known, whenever possible, based upon due diligence taken to obtain the follow-up information.

- **Pregnancies in Female Partners of Male Patients**

Tenecteplase-Icahn School of Medicine at Mount Sinai
Protocol ML42492

33

Male patients will be instructed through the Informed Consent Form to immediately inform the investigator if their partner becomes pregnant during the study or within 30 days after the last dose of study drug. A Clinical Trial Pregnancy Reporting Form should be completed and submitted to Genentech within thirty (30) calendar days of the awareness date.

In addition to all AEs, pregnancy reports and AESIs, the following Special Situations Reports should be collected and transmitted to Genentech/Roche even in the absence of an Adverse Event within thirty (30) calendar days:

- Data related to product usage during breastfeeding
- Data related to overdose, abuse, off-label use, misuse, inadvertent/erroneous administration, medication error (including potentially exposed in case of medication errors or intercepted medication errors) or occupational exposure, with or without association with an AE/SAE unless otherwise specified in the protocol
- Lack of therapeutic efficacy
- Drug interaction
- Use of a Medicinal Product in a Pediatric and Elderly population
- In addition, reasonable attempts should be made to obtain and submit the age or age group of the patient, in order to be able to identify potential safety signals specific to a particular population

Occasionally Genentech may contact the reporter for additional information, clarification, or current status of the patient for whom an adverse event was reported

- Product Complaints

All Product Complaints (with or without an AE) shall be forwarded to Genentech within fifteen (15) calendar days of the awareness date.

A Product Complaint is defined as any written or oral information received from a complainant that alleges deficiencies related to identity, quality, safety, strength, purity, reliability, durability, effectiveness, or performance of a product after it has been released and distributed to the commercial market or clinical trial.

5.4.5 MedWatch 3500A Reporting Guidelines

In addition to completing appropriate patient demographic and suspect medication information, the report should include the following information within the Event Description (Section 5) of the MedWatch 3500A form:

- Protocol description (and number, if assigned)
- Description of event, severity, treatment, and outcome if known
- Supportive laboratory results and diagnostics
- Investigator's assessment of the relationship of the adverse event to each investigational product and suspect medication

5.4.5.1 Follow-up Information

Additional information may be added to a previously submitted report by any of the following methods:

- Adding to the original MedWatch 3500A report and submitting it as follow-up
- Adding supplemental summary information and submitting it as follow-up with the original MedWatch 3500A form
- Summarizing new information and faxing it with a cover letter including patient identifiers (i.e., D.O.B. initial, patient number), protocol description and number, if assigned, brief adverse event description, and notation that additional or follow-up information is being submitted (The patient identifiers are important so that the new information is added to the correct initial report)

MedWatch 3500A (Mandatory Reporting) form is available at
<https://www.fda.gov/media/69876/download>

5.4.6 Reporting to Regulatory Authorities, Ethics Committees and Investigators

[name], as the Sponsor of the Study, will be responsible for the expedited reporting of safety reports originating from the Study to the Regulatory Authorities (FDA) where it has filed a clinical trial approval, in compliance with local regulations.

Genentech will be responsible for the expedited reporting of safety reports originating from the Study to the EMA through Eudravigilance Clinical Trial Module (EVCTM), where applicable.

[name] will be responsible for the distribution of safety information to its own investigators, where relevant.

Additional Reporting Requirements for IND Holders

For Investigator-Initiated IND Studies, some additional reporting requirements for the FDA apply in accordance with the guidance set forth in 21 CFR § 600.80.

Events meeting the following criteria need to be submitted to the Food and Drug Administration (FDA) as expedited IND Safety Reports according to the following guidance and timelines:

7 Calendar Day Telephone or Fax Report

The Investigator is required to notify the FDA of any fatal or life-threatening adverse event that is unexpected and assessed by the Investigator to be possibly related to the use of tenecteplase. An unexpected adverse event is one that is not already described in the tenecteplase Investigator Brochure. Such reports are to be telephoned or faxed to the FDA and Genentech within 7 calendar days of first learning of the event.

15 Calendar Day Written Report

The Investigator is also required to notify the FDA and all participating investigators, in a written IND Safety Report, of any serious, unexpected AE that is considered reasonably or possibly related to the use of tenecteplase. An unexpected adverse event is one that is not already described in the tenecteplase Investigator Brochure.

 Tenecteplase–Icahn School of Medicine at Mount Sinai
Protocol ML42492

35

Written IND Safety reports should include an Analysis of Similar Events in accordance with regulation 21 CFR § 312.32. All safety reports previously filed by the investigator with the IND concerning similar events should be analyzed and the significance of the new report in light of the previous, similar reports commented on.

5.5 AGGREGATE REPORTS

IND ANNUAL REPORTS

All IND annual reports submitted to the FDA by the Sponsor-Investigator should be copied to Genentech

Copies of such reports should be emailed to Genentech at: Genentech Drug Safety CTV mail box: [contact]

hyperlink to email:[contact]

Other Reports

[name] will forward a copy of the Publication to Genentech upon completion of the Study.

Note: Investigators should also report events to their IRB as required.

Randomization Codes for Blinded Clinical Trials

The blind will be broken for ADR reports that are Serious and Unexpected, unless otherwise agreed with applicable regulatory authorities.

5.6 STUDY CLOSE-OUT

Any study report submitted to the FDA by the Sponsor-Investigator should be copied to Genentech. This includes all IND annual reports and the Clinical Study Report (final study Tenecteplase-Icahn School of Medicine at Mount Sinai Protocol ML42492

report). Additionally, any literature articles that are a result of the study should be sent to Genentech. Copies of such reports should be mailed to the assigned

Clinical Operations contact for the study: [contact]

hyperlink to email: [contact]

[contact]

And to Genentech Drug Safety CTV oversight mail box at: [contact]

hyperlink to email: [contact]

QUERIES

Queries related to the Study will be answered by [name]. However, responses to all safety queries from regulatory authorities or for publications will be discussed and coordinated between the Parties. The Parties agree that Genentech shall have the final say and control over safety queries relating to the Product. [name] agrees that it shall not answer such queries from regulatory authorities and other sources relating to the Product independently but shall redirect such queries to Genentech.

Both Parties will use all reasonable effort to ensure that deadlines for responses to urgent requests for information or review of data are met. The Parties will clearly indicate on the request the reason for urgency and the date by which a response is required.

6. STATISTICAL CONSIDERATIONS

6.1 DETERMINATION OF SAMPLE SIZE

Assuming a total of 60 subjects enrolled with a 2:1 ratio in the tenecteplase:control arms and a good outcome rate of 15% in the control arm, this study has approximately 70% power to detect an absolute difference of 35% in the good outcome rate between the combined tenecteplase arms (40 patients) and the control arm (20 patients) and approximately 55% power to detect an absolute difference of 35% between each of the tenecteplase arms (20 patients) and the control arm (20 patients), at the 2-sided 0.05 significance level based on the Fisher's exact test. Good outcome rate is defined as the proportion of patients who are alive and free of respiratory failure at 28 days. If the true rate of symptomatic ICH or major bleeding requiring transfusion is 3%, the chance of observing at least one of these events in 20 patients is at least 45%. The chance of observing at least one event in 20 patients increases to at least 70% if the true event rate is 6%.

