6.5 METHOD OF ANALYSIS

Continuous and categorical variables will be presented and summarized by using means with standard deviations and frequencies with percentages respectively. Tukey's method for pairwise comparison and large sample based multiple comparison of logits will be performed for continuous variables. Logistic regression modeling will be used for covariates adjustments and subgroup analyses. Survival functions will be estimated by applying Kaplan-Meier method. Statistical testing will be performed at two-sided 5% level of significance.

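### Section 6.5 names no test for the 28-day good-outcome proportions; Boschloo's exact test would hold 5% per comparison and, at the plan's own inputs, give more power than the Fisher's test assumed in 6.1 (74.5% to 78.2% combined, 57.3% to 66.1% per dose)

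*Combined protocol and SAP*

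**What the plan says.** Section 6.1 starts from "Assuming a total of 60 subjects enrolled with a 2:1 ratio in the tenecteplase:control arms". Its other planning input is "a good outcome rate of 15% in the control arm". It claims "approximately 70% power to detect an absolute difference of 35% in the good outcome rate" for the two doses combined (40) against control (20), and "approximately 55% power to detect an absolute difference of 35% between each of the tenecteplase arms" (20) and control (20). Both figures are "at the 2-sided 0.05 significance level based on the Fisher's exact test".

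Section 6.2 defines the outcome and the handling of missing data, but names no test. Section 6.5 says "Statistical testing will be performed at two-sided 5% level of significance". It mentions Tukey's method, a large-sample comparison of logits (attached to continuous variables) and logistic regression for covariates and subgroups. It does not mention Fisher's test or any other test of the unadjusted proportions, and it does not say which of the three comparisons is primary. Section 3.3 says the study is not powered for significance and is meant to estimate a benefit signal for a phase III trial.

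**The concern.** Fisher's test is the only test the document ties to the good-outcome comparison, so it is the likely default once data are in. It conditions on both margins of the 2x2 table. With 20 to 40 patients per group few p-values are attainable, so the real error rate falls well short of the declared 5%. The shortfall is paid for in power, and most heavily in the per-dose comparisons, which are the smallest and bear on the choice of dose for phase III.

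Because 6.5 leaves the test open, the choice could also be made after the results are known. Naming a test in advance closes that gap, and there is then reason to name one that uses more of the 5%.

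**Working it through.** **Inputs (Section 6.1).** Two-sided level 0.05; n1 = 40 or 20 on tenecteplase, n0 = 20 on control; p0 = 0.15; p1 = 0.15 + 0.35 = 0.50.

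**Method.** Treat the groups as independent binomials and list every table (x, y). For a rejection region R:

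- Power = sum over R of Bin(x; n1, p1) × Bin(y; n0, p0).
- Size = the maximum over a common rate p of the sum over R of Bin(x; n1, p) × Bin(y; n0, p).
- Fisher: R = tables with two-sided Fisher p ≤ 0.05.
- Boschloo: R = tables with Fisher p ≤ c, where c is the largest value that keeps the size at or below 0.05.

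**Step 1: the plan's own figures.** Fisher's power for 40 v 20 is 71.4% if the smaller tail is doubled, or 74.5% if tables no more likely than the observed one are summed (the usual software default). For 20 v 20 it is 57.3% either way. The stated 70% and 55% agree with 71.4% and 57.3% rounded to the nearest 5. They are approximate and slightly low, and are not a planning error.

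**Step 2: Fisher against Boschloo** (usual Fisher convention).

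| | 40 v 20 | 20 v 20 |
|---|---|---|
| Fisher, maximum type I error | 3.7% | 2.5% |
| Boschloo, critical Fisher p (c) | 0.0575 | 0.0915 |
| Boschloo, maximum type I error | 4.9% | 4.6% |
| Fisher, power at 15% v 50% | 74.5% | 57.3% |
| Boschloo, power at 15% v 50% | 78.2% | 66.1% |
| Gain | 78.24 − 74.48 = 3.8 points | 66.13 − 57.34 = 8.8 points |

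Both values of c exceed 0.05, so every table that Fisher's test rejects is also rejected by Boschloo's. Ordering tables by the one-sided Fisher p instead gives 79.0% for 40 v 20 and the same 66.1% for 20 v 20.

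**Step 3: an example.** For 9/20 v 3/20 good outcomes, Fisher p = 0.082 and Boschloo p = 0.042.

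**Step 4: three tests together.** The two doses share one control arm. If all three comparisons are tested at 0.05 without adjustment, the chance of at least one false rejection, at its maximum over the common rate, is 5.7% with Fisher and 8.8% with Boschloo. At a common rate of 15% it is 5.0% and 7.2%.

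**Step 5: drift between stages.** Section 4.2 enrols the low dose first and the high dose second, with 10 of the 20 controls in each stage. Each 20 v 20 comparison therefore uses 10 concurrent and 10 non-concurrent controls. As an assumption, suppose the good-outcome rate moves between stages with no drug effect. The type I error of the high-dose comparison is then:

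| First stage to second stage | Fisher | Boschloo |
|---|---|---|
| 15% to 25% | 3.2% | 6.0% |
| 15% to 30% | 4.3% | 7.5% |

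**Step 6: gating the doses on the combined test.** With control at 15% and high dose at 50%, the power to declare the high dose, using Boschloo's test throughout, depends on the low dose:

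| True low-dose rate | High-dose power, gated Boschloo | High-dose power, ungated Fisher |
|---|---|---|
| 15% | 24.5% | 57.3% |
| 25% | 38.8% | 57.3% |
| 35% | 52.4% | 57.3% |
| 50% | 63.7% | 57.3% |

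**The case against.** The strongest case on the other side has four parts.

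- **The plan does not adopt Fisher's test as its analysis.** This stands. The test appears only in the power statement, where a conservative choice is legitimate. A reader might infer that the plan has chosen a poor primary test, but 6.5 names none. The gap is the missing test, and Boschloo's is a better candidate than the default.
- **The extra power is not free.** This also stands. Rejecting whenever Fisher's test does, within 5%, is a property of each comparison taken singly. With three unordered tests the familywise error rises (Step 4). An obvious remedy is to test the doses only after a significant combined result, but Step 6 shows that this can cost far more than Boschloo's test gains when the doses differ, which a dose-escalation trial should be able to show. It also gives no rule if escalation stops after the low dose and no 40 v 20 comparison exists.
- **Fisher's slack protects against drift.** True in part (Step 5), though the protection is incidental and limited: at a drift from 15% to 35% Fisher's own error reaches 5.8%.
- **The trial seeks a signal and is not powered for significance.** This limits the importance of the point. But the plan still quotes power and tests at 5%, so a named test with better use of that 5% remains worthwhile.

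A reader might also expect gains of 8 points combined and 11 per dose. Gains that large, like for like, need a control rate near 30% (65.9% to 74.2%, and 46.8% to 57.8%), which the documents do not assume.

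**Conclusion.** The plan should name its test for the primary proportions, and Boschloo's exact test is a better choice than the Fisher's test used for planning. At the plan's own inputs the gain is 3.8 points of power for the combined comparison and 8.8 points for each dose, with the maximum type I error of each comparison at 4.9% and 4.6%.

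This rests on independent binomial outcomes, full enrolment of 40 and 20, one control rate across both dose stages, and an analysis that is not stratified by site, although randomisation is. It holds per comparison. The documents do not support the stronger conclusions that Fisher's test is the planned analysis, that the stated power is wrong, or that the gain carries over at no cost to all three tests together. The effect on the trial's conclusions is moderate, since its stated aim is estimation.

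**What to change.** Before unblinding:

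1. In 6.5, name combined tenecteplase v placebo on the 28-day good outcome as the single primary comparison, tested with Boschloo's exact test at two-sided 0.05 wherever the analysis is not site-stratified. State the ordering used (two-sided or one-sided Fisher p), since the power for 40 v 20 differs slightly between them.
2. Report each dose v placebo with Boschloo's test as secondary, with the estimated difference and its confidence interval, and without a familywise claim. Do not make these tests conditional on the combined result.
3. In 6.1, restate power as 78.2% (combined) and 66.1% (each dose) for 15% v 50%, with the ordering that gives these figures.
4. State the downsides: the test is less familiar; familywise error could reach 8.8%, against 5.7% with Fisher, if all three tests were read as confirmatory; and there is less slack against drift, because half of each dose's controls are non-concurrent.

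The cost is a few sentences of plan text and one line of code. It needs no extra patients or data and changes no trial procedure.
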